1 STUDY SUMMARY

1.1 Protocol summary

Title:	Treating Oesophageal Atresia to prevent Stricture (TOAST)
Short title:	TOAST feasibility study
REC number:	8510
Funder name and reference:	NIHR Health Technology Assessment Programme reference: NIHR131136
Study design:	Mixed methods
Study objectives:	
1. To review and explore acceptability of the proposed trial2. To review and explore potential barriers and solutions to recruitment and approaches to consent, including acceptability of an opt-out consent model, timing of approach, parental decision making, practitioner equipoise, trial information materials and practitioner training needs3. To review and explore with parents important, parent-centred, primary and secondary outcomes for a definitive RCT
Recruitment	We will recruit parents and practitioners through online routes and our networks
Population:	Parents of recent infants born with oesophageal atresia, including those with/without stricture and those who did/did

This project was funded by the National Institute for Health Research Health Technology Assessment Programme (project number NIHR 131136). The views and opinions expressed therein are those of the authors and do not necessarily reflect those of the HTA Programme, NIHR, NHS or the Department of Health.

	not receive routine antacid medication. Medical practitioners (surgeons and neonatologists) and nurses (neonatal surgical specialist nurses) caring for infants with oesophageal atresia.
Planned sample size:	15-25 parents and at least 50 practitioners from approximately 18/25 (75%) of UK units
Duration:	9 months
Follow up duration:	No follow up
Planned study period:	March 2021- November 2021

This project was funded by the National Institute for Health Research Health Technology Assessment Programme (project number NIHR 131136). The views and opinions expressed therein are those of the authors and do not necessarily reflect those of the HTA Programme, NIHR, NHS or the Department of Health.

2 BACKGROUND INFORMATION

2.1 Introduction and rationale

What is the problem being addressed?

Oesophageal atresia is a rare congenital anomaly affecting 1 in 2,500–3,000 live-born babies worldwide, approximately 150 cases/year in the UK [1]. Previously a condition with high mortality, survival has improved and the focus has shifted from ensuring survival to reducing morbidity, achieving excellent clinical outcomes and optimising quality of life. In this context, it is imperative to assess interventions consistent with these new aims particularly since affected infants may have a multiple morbidities due to a number of co-existing medical problems. Infants who develop an anastomotic structure typically require admission to hospital for investigation followed by a surgical procedure. The standard approach to treating a stricture is dilatation of the narrowed segment, where the narrowing is mechanically stretched open, which is performed under general anaesthesia.

Determining if routine antacid medication reduces the incidence or severity of anastomotic stricture in infants with oesophageal atresia is imperative if we are to understand how to best treat these infants and optimise their chances of the best possible outcomes. As a rare disease, conditions like oesophageal atresia are often overlooked in research agendas, yet current variation in practice is not justifiable nor evidence based. This was recognised in the evidence review that informed the commissioning brief for this commissioned call. We believe it is imperative to rigorously investigate the effectiveness of interventions in infants with oesophageal atresia in our objective to provide them with the best possible outcomes.

As such, if routine antacid medication were found to be effective at reducing incidence or severity of strictures surgeons would be able to confidently prescribe antacid medication and, importantly, their use could be justified in all infants following oesophageal atresia repair. Given the minimal cost of antacid medication, the intervention is likely to be cost effective if clinically effective. Conversely, if found to be ineffective or even harmful, routine use of antacid medication should be avoided. In addition to the clinical justification for this research there is also an economic argument to be made for both the healthcare system, society and families of affected infants. A reduction in number of dilatations even a median of one dilatation per oesophageal atresia case would result in significant savings to the healthcare sector and wider society over time.

This project was funded by the National Institute for Health Research Health Technology Assessment Programme (project number NIHR 131136). The views and opinions expressed therein are those of the authors and do not necessarily reflect those of the HTA Programme, NIHR, NHS or the Department of Health.

A review of the literature relating to the use of antacid medication in infants with OA reveals that the existing evidence stems from only a small number of observational studies. There are no published RCTs on this matter. There is a very clear need to 1) understand the role of antacid medication in the care of infants with oesophageal atresia, 2) generate high-grade evidence to advise guideline generating bodies for or against the recommendation of antacid medication, 3) to equip health-care providers with reliable knowledge, derived from performing a large RCT on the use of antacid medication, to, ultimately, 4) allow for uniform, standardised postoperative treatment of infants born with oesophageal atresia. The generation of this knowledge would help to avoid confusion among care-providers and parents concerning the validity of antacid medication prescription in this patient group and ultimately generate a better understanding of antacid medication's role in the development of strictures to significantly benefit patients, families and the healthcare system.

Clinical trials, such as the proposed TOAST trial, are expensive and the chances of successful completion are improved if they are deemed to be acceptable to families and practitioners and feasibility and pilot testing of certain key parameters can be clearly demonstrated.

2.2 Aims and objectives

Aim

To undertake a mixed-methods feasibility study involving practitioners and parents to inform the design and successful conduct of the TOAST trial.

Objectives:

1. To review and explore acceptability of the proposed trial including population of infants for inclusion, type, dose and duration of antacid medication and treatment pathways
2. To review and explore potential barriers and solutions to recruitment, retention and approaches to consent, including acceptability of an opt-out consent model, wording

This project was funded by the National Institute for Health Research Health Technology Assessment Programme (project number NIHR 131136). The views and opinions expressed therein are those of the authors and do not necessarily reflect those of the HTA Programme, NIHR, NHS or the Department of Health.

- and format of information materials, timing of approach, parental decision making, practitioner equipoise, trial information materials and practitioner training needs
3. To review and explore with parents important, parent/family centred, primary and secondary outcomes for a definitive RCT.

3 STUDY DESIGN AND CONDUCT

3.1 Study design and setting

We will use a mixed methods study design including a survey, interviews and a focus group and practitioners and interviews with parents. This feasibility work will be led by [name] (KW) and the TOAST Research Associate (RA).

3.2 Eligibility criteria

Inclusion criteria:

Parents of recent infants born with oesophageal atresia, including those with/without stricture and those who did/did not receive routine antacid medication in the last three years.

Medical practitioners (surgeons and neonatologists) and nurses (neonatal surgical specialist nurses) caring for infants with oesophageal atresia.

Exclusion criteria:

Parents/Legal representatives who do not speak English.

3.3 Recruitment and sampling

Parents

The research associate (RA) will contact gatekeepers (e.g. charity leads/Chief Executive Officers) of patient support groups for oesophageal atresia infants and ask them to place the TOAST online recruitment advert on the support group's website and/or social media pages. The RA will also send targeted invitations via support group websites, including our collaborating charity TOFS (<https://www.tofs.org.uk/home.aspx>), and disseminate the advert widely on relevant social media pages for OA infants using hashtags and tagging.

The online advert will contain information and contact details for parents to register their interest in taking part in an interview. TOFS will also send a TOAST email invitation to

This project was funded by the National Institute for Health Research Health Technology Assessment Programme (project number NIHR 131136). The views and opinions expressed therein are those of the authors and do not necessarily reflect those of the HTA Programme, NIHR, NHS or the Department of Health.

participate to their members. A link to the study website (insert link) will provide additional information about the study, including the Participant Information Sheet (PIS).

Practitioners

We will send email invitations including study PIS via our networks/national associations and use social media to invite a mix of surgeons/neonatologists/specialist nurses from a range of UK hospitals to complete an online survey and/or register their interest in taking part in an online focus group. Social media adverts will include a description the purpose of the study, what is involved, a link to the survey and RA contact details to register interest in an interview or focus group. A link to the study website will provide additional information about the study including the PIS.

We will purposively sample approximately 5-7 questionnaire participants who raise concerns about the proposed trial design and invite them to participate in a telephone interview. The interviews will aim to further explore their concerns and discuss potential ways these could be addressed to assist 'buy in'. Findings from the online survey, practitioner interviews and parent interviews will be used to inform the practitioner focus group topic guide with specific issues and potential solutions discussed to inform the trial design.

Additional social media advertising and emails may be used to recruit to the focus group if an insufficient sample (e.g. less than 8-10 people) are recruited via questionnaire completion.

Arranging interviews and focus group

The RA will check eligibility and send a PIS to all parents and practitioners who register interest in participating. The RA will then arrange a suitable time for an online interview or focus group (practitioners only) via Zoom or Microsoft Teams.

A copy of the draft TOAST trial Participant Information Sheet and TOAST outcomes list will be sent to parents via email. Parents/Legal representatives will be asked to read this PIS and outcomes list before the scheduled interview. Parents/Legal representatives who do not meet the eligibility criteria, or register after the target sample size (15-25 depending upon data saturation point) has been reached, will be thanked for their time and will take no further part in the study.

This project was funded by the National Institute for Health Research Health Technology Assessment Programme (project number NIHR 131136). The views and opinions expressed therein are those of the authors and do not necessarily reflect those of the HTA Programme, NIHR, NHS or the Department of Health.

A similar process will be followed to arrange practitioner interviews and focus group although a brief outline of the proposed trial will be shared prior to interview rather than PIS and outcomes list described above.

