3.7 Sample size

We will use snowball sampling for the practitioner survey and aim to include approximately 50 practitioners representing 75% of UK units (e.g. 18/25 of the UK units). Interviews will be conducted with 5-7 questionnaire participants. We anticipate 8-10 medical practitioners and nurses caring for children with oesophageal atresia infants will attend the focus group.

Parent interviews will continue to be conducted until data saturation is reached. This is when the major themes identified in new data are reoccurring from previous participants/transcripts and no new major themes are being discovered. Based on previous, similar studies [1-3] this is anticipated to be approximately 15-25 parents/legal representatives.

Data analysis

Interviews and focus groups will be transcribed, checked and anonymised as the study progresses. QSR NVivo software will be used to assist in the organisation and indexing of qualitative data. Whilst reflective thematic analysis[4, 5] will be informed by the constant comparison approach of grounded theory, the focus will be modified to fit with the criterion of catalytic validity, whereby findings should be relevant to future research and practice (i.e. the design of the TOAST trial). Findings from the interviews and focus groups will be fed into the design (including patient information materials), approach to consent and training for site investigators.

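### Nothing in the parent selection, closing or stopping rules secures the mix of stricture and routine-antacid families that the population describes

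*Protocol*

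**What the plan says.** Protocol section 3.2 defines the parents as those of recent infants with oesophageal atresia, "including those with/without stricture and those who did/did not receive routine antacid medication". The summary in section 1.1 names the same two characteristics.

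Section 3.3 recruits parents through several patient support groups, an email from the collaborating charity, and social media. "The online advert will contain information and contact details for parents to register their interest in taking part in an interview". It adds: "The RA will also send targeted invitations via support group websites". The targeting is by channel; stricture and antacid status are not mentioned. For those who come forward, "The RA will check eligibility and send a PIS to all parents and practitioners who register interest in participating", and an interview time is then arranged. Parents who are ineligible, or who "register after the target sample size (15-25 depending upon data saturation point) has been reached, will be thanked for their time", take no further part.

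Section 3.7 gives the stopping rule: "Parent interviews will continue to be conducted until data saturation is reached". Saturation means that major themes are recurring and "no new major themes are being discovered". The expected number, about 15-25, is taken from previous similar studies.

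For practitioners, section 3.3 plans purposive sampling of 5-7 survey respondents with concerns and seeks a spread of professions and hospitals. Section 3.7 adds a coverage aim of 18 of 25 UK units. Parents have no counterpart to any of these.

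**The concern.** The population statement names both sides of two characteristics that bear directly on the planned trial, which is to test whether routine antacid reduces stricture. The rules that decide who is interviewed take no account of either. A sample containing no parent of an infant who went without routine antacid would comply fully with the protocol.

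This goes further than a missing detail, because the protocol fixes a closing rule. Once the target is met, a parent from an unheard group who registers late is declined. The saturation rule does not protect against this. A homogeneous set of parents can stop yielding new themes early, so under-representation may bring closure forward.

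At stake is how far the parent findings can be generalised. Section 2.2 asks parents about acceptability, decision making and outcomes. Section 3.7 feeds the findings into design, information materials and consent, and section 10.2 reports them as parents' views. If experience of stricture or antacid shapes those views, readers need to know whose views they are.

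**Working it through.** **The plan's own figure.** The 15-25 rests on a saturation judgement and on previous studies (section 3.7). It has no formula behind it, so there is nothing to reproduce.

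**Tracing the rules.** At each step that decides who is interviewed, does the text refer to stricture or antacid status?

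- Population (1.1, 3.2): yes, both are named.
- Advertising and invitations (3.3): no.
- Eligibility check and booking (3.3): only through the inclusion criterion, which both sides of each pair satisfy.
- Closing to new registrants (3.3): no.
- Stopping (3.7): no.

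**Sizing the risk.** Inputs: n = 15, 20 or 25 interviews (the protocol's range and its midpoint). The share p of registrants belonging to a given group is not in the protocol, so p = 5% to 30% is assumed. Interviewed parents are treated as independent draws with constant p, and n is treated as fixed.

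Chance that the group is absent: P(0) = (1 - p)^n.

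- p = 10%: 0.90^15 = 0.206; 0.90^25 = 0.072.
- p = 20%: 0.80^15 = 0.035; 0.80^25 = 0.004.

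Chance of two or fewer: P(≤2) = (1 - p)^n + n p (1 - p)^(n-1) + [n(n-1)/2] p^2 (1 - p)^(n-2).

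- p = 10%, n = 15: 0.206 + 0.343 + 0.267 = 0.816.

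| Assumed share | None: n = 15 / 20 / 25 | Two or fewer: n = 15 / 20 / 25 |
|---|---|---|
| 5% | 46% / 36% / 28% | 96% / 92% / 87% |
| 10% | 21% / 12% / 7% | 82% / 68% / 54% |
| 20% | 3.5% / 1.2% / 0.4% | 40% / 21% / 10% |
| 30% | 0.5% / 0.08% / 0.01% | 13% / 4% / 1% |

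Complete absence is a material risk at shares of about 10% or less and negligible from 30% upward. Thin representation persists at larger shares, mainly when the study closes near 15.

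**The case against.** Four points can fairly be made for the plan.

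- **The population statement may only be permissive.** Every eligible family falls on one side of each pair, so the wording can mean that nobody is excluded on these grounds. A reader might infer that the protocol requires each group, or all four combinations of stricture and antacid. It does not: no minimum, stratum or comparison is promised. This stands, so the point is a gap between description and rules, not a contradiction.
- **No order of selection is written.** A reader might infer first come, first served. The text states no queue. It says only that eligible registrants are booked and later ones declined. Priority for earlier registrants is an effect of the closing rule. This also stands.
- **Closure depends on saturation as well as a count.** Transcription runs as the study progresses, and the analysis draws on constant comparison, so a parent from a rarer group who raises a new major theme would keep interviewing open. That is true once such a parent has been interviewed. It does nothing for a group that has not been reached.
- **The larger probabilities need small shares that nothing in the protocol supports.** Section 2.1 speaks of variation in current practice, which sits poorly with a nearly empty antacid or no-antacid group, though it gives no figure. Recruitment also uses several support groups and social media, not one charity. This limits the size of the risk but does not remove the gap, because no rule would reveal a shortfall before closing.

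A reader might also conclude that objectives 1 to 3 will be biased. The documents do not show that views differ by group, the objectives are exploratory, and practitioner data inform the design too. The supportable claim is that the plan can close short of a group, not that it will.

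**Conclusion.** The point holds as a cheap improvement. The parent population is described by stricture and routine-antacid status, and no selection, closing or stopping rule secures that mix. The protocol's own text establishes this without any assumption about shares.

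The size does rest on assumptions: independent registrants, a fixed number of interviews and unknown group shares. With a 10% share, the chance of no parent from the group is 21% at 15 interviews and 7% at 25; with 20%, 3.5% and 0.4%; with 30% or more, negligible. Whether the true shares are near the low end cannot be told from the protocol.

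**What to change.** In sections 3.3 and 3.7:

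1. Record stricture status and routine-antacid status for each parent at the eligibility check that the research associate already makes.
2. Select parents purposively from registrants for variation on both characteristics, within the same 15-25 interviews.
3. Amend the closing rule so that a late registrant from a group not yet represented is not declined, and hold other surplus registrants on a reserve list meanwhile.
4. Report the mix achieved, and name any group that stayed short, wherever parents' views are described.

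Saturation can remain a single overall judgement. Requiring it within each group would not fit inside 15-25 interviews. Whether to set a minimum per group, and at what number, is for the sponsor.

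The cost is two questions at registration, about a paragraph of protocol text and one reporting line, with no increase in the planned number of interviews. The downside is that some registrants wait on a reserve list and recruitment may run slightly longer.

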3.4 Informed consent

Practitioner questionnaire

At the beginning of the questionnaire a series of consent statements and check boxes will be used to seek consent for participation.

Telephone interviews

The RA will begin the telephone interview by explaining the aims of the study, providing an opportunity for questions and verbally obtaining informed consent for the study. This will involve the RA reading each aspect of the TOAST Practitioner Consent Form to participants, including consent for audio recording and to receive a copy of the findings when the study is complete. The RA will tick each box on the consent form when the participant provides verbal consent. Informed consent discussions will be audio recorded for auditing purposes.

After the interview is complete the RA will sign the consent form and send a TOAST Feasibility study Participant thank you letter including a copy of consent form. Parents will be sent a £30 Amazon voucher to thank them for their time.

Practitioner focus group

The consent form will be emailed to practitioners in advance of the focus group and written informed consent will be sought. Practitioners will be asked to electronically sign the consent form and return it to the RA via email before the scheduled focus group.

3.5 Questionnaire conduct

The questionnaire will be on an online platform (e.g. Survey Monkey or Quatrics) and contain researcher derived questions to address the study aims. This will include an outline of the trial and questions to assess views on trial acceptability, inclusion/exclusion criteria as well as crucial 'buy in'.

This project was funded by the National Institute for Health Research Health Technology Assessment Programme (project number NIHR 131136). The views and opinions expressed therein are those of the authors and do not necessarily reflect those of the HTA Programme, NIHR, NHS or the Department of Health.

3.6 Focus group and interview conduct

Parent interview conduct

The RA will check that the parent has had sufficient time to read the example TOAST Pilot Study Participant Information Sheet. The interview will then commence using the interview topic guide which will explore parents' views on:

- acceptability of the proposed trial design and procedures such as type and dose, frequency, delivery and length of trial intervention;
- wording and format of participant information materials;
- consent decision-making; the approach to parents regarding enrolment and consenting processes;
- potential barriers to recruitment and retention; and
- parent/family-centred primary and secondary outcome measures for a definitive trial.

Practitioner focus group and interview conduct

Practitioner focus group and interview topic guides will be developed using early parent interview and practitioner questionnaire findings.

Consent will also be checked verbally before the focus group begins including consent for recording the focus group. The focus groups will commence using the focus group topic guide to explore clinicians' views on:

- trial feasibility and acceptability;
- design aspects and additional clinical questions, such as type, dose and delivery of trial intervention; and
- equipoise of clinicians, including willingness of clinicians to approach parents to participate/randomise infants and practitioner training needs.

For interviews the RA will use an interview topic guide to cover the same areas outlined for focus groups but will also draw on the participants questionnaire responses, requesting further details of concerns raised and discussing any potential changes to the trial design or conduct that may help address such concerns.

